1.0 INTRODUCTION

1.1 OBJECTIVES

PRIMARY STUDY OBJECTIVES:

1.1.1 To assess the effect of R115777, administered on a chronic oral schedule (21 days on followed by 7 days rest), on the time to disease progression in children and young adults with neurofibromatosis type 1 (NF1) and progressive plexiform neurofibromas.

- 1.1.2 To define the objective response rate of progressive plexiform neurofibromas to R115777.
- 1.1.3 To describe and define the toxicities of R115777, administered on a chronic oral schedule (21 days on followed by 7 days rest), in pediatric patients and young adults.

SECONDARY STUDY OBJECTIVES:

- 1.1.4 To measure the level of farnesylprotein transferase (FPTase) activity in tumor specimens and peripheral blood mononuclear cells obtained from patients treated on this trial, and to assess the value of FPTase activity as a surrogate marker for the antiproliferative effect of R115777.
- 1.1.5 To assess the value of three-dimensional MRI (3D-MRI) and unidimensional MRI (1D-MRI) data analysis in the evaluation of plexiform neurofibromas, and to compare both to conventional two-dimensional MRI (2D-MRI) data analysis.
- 1.1.6 To analyze tumor specimens from patients with NF1 treated with R115777 for the level of expression of N-*ras*, K-*ras*, and H-*ras*, and to correlate the level of expression and the *ras* mutation status with the efficacy of R115777.
- 1.1.7 To analyze tumor specimens from patients treated on this trial, for NF1 gene mutations in the GAP related domain, and to correlate these findings with the antiproliferative effect of R115777.
- 1.1.8 To establish tumor cell lines from tumor specimens (plexiform neurofibromas and discrete neurofibromas) obtained from patients treated on this trial.
- 1.1.9 To contribute tumor specimens obtained on this trial to an already existing tissue bank. Tumor samples from plexiform neurofibromas will undergo a central pathology review including a detailed morphologic, ultrastructural and immunohistochemical analysis. Tumor cell lines and tumor samples will be made available to the scientific community, after obtaining IRB approval in order to collect more information on the

pathology, genetics, and cell biology of plexiform and discrete neurofibromas.

- 1.1.10 To determine circulating levels of nerve growth factor from blood samples at various time points during treatment with R115777/placebo, and to correlate levels of NGF with the development of clinical neurotoxicity from R115777.

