1.2.7 CLINICAL PHARMACOKINETICS OF R115777 IN ADULTS AND CHILDREN

Pharmacokinetic analysis of plasma samples from 19 patients treated on an adult phase I trial with R115777 revealed:

- R115777 is rapidly absorbed after oral administration (time to peak was approximately 2-4 hours). The bioavailability of the capsules increased when given after a meal.
- The concentrations of R115777 decline biphasically with an initial, dominant half-life of about 2-3 hours and with a median terminal $T_{1/2}$ of about 6 hours;
- Over the dosage range studied to date the pharmacokinetics of R115777 appear to be linear;
- The average accumulation ratio of R115777 was calculated at 1.1, and therefore minimal accumulation is expected on the q12 hr dosing regimen.
- In healthy human adults plasma protein binding of R115777 was very high, with a free fraction of 0.66-0.77%.
- In human hepatocytes glucuronidation of R115777 at the imidazole nitrogen was the major metabolic pathway.

Pharmacokinetic analysis of oral R115777 has also been performed on plasma samples from 30 children (median age 13 years, age range 5 to 17 years) treated on our pediatric phase I trial. In general the pharmacokinetics of R1157777 are similar in adults and children. Preliminary observations regarding the plasma pharmacokinetics of R115777 in pediatric patients are:

• R115777 is rapidly absorbed after oral administration: The average time to peak concentration was 2.7 hours (range 1.0 –8.0 hours);

- The Average terminal half-life was 6.8 hours (range 2.8-16.7 hours) The determination of $T_{1/2}$ was limited by the 36-hr sampling and highly dependent on the ability to quantify low concentrations of R115777 in the terminal phase;
- Over the dosage range studied to date the pharmacokinetics of R115777 appear to be linear: The average AUC increased from 4318 ng•h/ml (± 1763) at the 150 mg/ m² dose level to 13536 ng•h/ml (± 7831) at the 375 mg/ m² dose level. The C_{max} increased from 1034 ng/ml (± 566) at the 150 mg/ m² dose level to 2433 ng/ml (± 730) at the 375 mg/ m² dose level.
- Minimal accumulation is expected on the q12 hr dosing regimen.

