3.1.8 FPTASE ACTIVITY IN PBMC

FPTase activity will be assessed in PBMCs pretreatment and once between days 15 and 21 of treatment (steady state) on cycle #1 of each treatment phase ("A" and "B") as a surrogate marker for the effect of R115777 (Appendix 5). PBMCs should be obtained at the same time as tumor biopsies in patients who consent to a biopsy.

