3.3 MODIFICATIONS FOR TOXICITY

Patients who experience **grade 2 toxicity** (CTC v. 2) related to R115777 or placebo should have R115777/placebo withheld until the toxicity resolves (grade \leq 1) and then restarted at the same dose level. If the grade 2 toxicity recurs, the R115777/placebo dose should be withheld again until the toxicity resolves (grade \leq 1) and then reduced by 50 mg per dose. For patients with a BSA \leq 0.37 the dose will be reduced to 50 mg once daily. If the grade 2 toxicity recurs the patient should be taken off protocol. If a grade 2 toxicity persists for >10 days off therapy, the patient should be discussed with the PI.

Patients who experience **grade 3 or 4 toxicity** related to R115777 or placebo should have their dose withheld. If the toxicity returns to grade ≤ 1 within 10 days, patients may resume R115777/placebo at a dose reduced by 50 mg per dose. For patients with a BSA ≤ 0.37 the dose will be reduced to 50 mg once daily. If the toxicity persists at grade ≥ 2 for >10 days without administration of R115777/placebo or the grade 3 or 4 toxicity recurs at the lower dose level, the patient should be removed from the study (see Section 3.6.2).

If the toxicity warrants, the physician can determine whether the patient is receiving R115777 or placebo (unblind the study) by calling [name] [contact] or [name] [contact]. These physicians can also be reached through [contact] or the NIH page operator [contact] (see section 8.2.5). Pediatric Oncology Branch staff will require the protocol number (i.e., 'T99-0090'), the patient's ID number (e.g., '00-C0222-01'), the phase (i.e., 'A' or 'B'), and the patient's

initials (first three letters of last name, eg., 'ABC') to unblind the patient. The unblinded patient must be removed from the study.

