- 3.4.7 FPTase ACTIVITY IN PBMC: PBMC should be collected pretreatment, and once between days 15 and 21 of treatment (steady state) on cycle #1 of each treatment phase ("A" and "B"). If the patient has consented to a tumor biopsy, PBMCs should be obtained at the same time as the biopsy (Section 3.4.6). PBMC should be separated from 20 ml of blood (10 ml in children \leq 10 kg) as described in Appendix 5.
- 3.4.8 Nerve Growth Factor: A blood sample will be collected pretreatment, and prior to cycles 4, 7, 10, and then after every six cycles on each treatment phase ("A", "B"). Nerve growth factor levels will be correlated with the development of clinical neurotoxicity (Appendix 6).
- 3.4.9 QUALITY OF LIFE (QOL) ASSESSMENT: The National Institutes of Health (NIH) Impact of Pediatric Illness (IPI) Scale, which assesses the impact of disease and treatment on children's behavior, should be administered to all patients ≥6 years to 18 years of age and their primary caregiver prior to the start of therapy, and then prior to cycles 4, 7, 10, and then after every 6 cycles on each treatment phase. This questionnaire has not been completely validated, and means and standard deviations for different subgroups of patients on the scale and subscales are not available yet. This assessment

consists of an age-appropriate questionnaire and generally takes less than 30 minutes to complete. Patients between the ages of 6 and 10 years of age should be administered the IPI-Young Child form; patients between 11 and 18 years of age should be administered the IPI-Older Child/Adolescent form; the patient's primary caregiver should receive the IPI-Parent Form. This questionnaire will not be administered to patients > 18 years. Patient and parent response forms should be photocopied after completion and copies sent to [name], Pediatric Oncology Branch, NCI, [contact], [name], Bethesda, MD 20892-1928 within 2 weeks of completion of the cycle of therapy. Any questions regarding the administration of the IPI Scale should be addressed to [name]. at [contact], e-mail: [contact].

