APPENDIX 5: PROCEDURE PBMC SEPARATION FOR FARNESYLTRANSFERASE ACTIVITY

PBMC Collection Steps:

• Collect peripheral blood (20 ml in children >10 kg weight, 10 ml in children ≤10 kg weight) in preservative free heparin (10-20 units heparin/1ml of blood).

- Place peripheral blood in polypropylene screw top tube(s).
- Label tube with: Patient initials, Patient ID number, date, treatment phase ("A", "B"), and day of treatment (pre, day 15-21).

Shipment Of Peripheral Blood:

- Place tube(s) in container.
- Place the container with the polypropylene tube(s) in Styrofoam box. Add a package of wet ice in Styrofoam box, if it is expected that the ambient temperature cannot be maintained between below 90 ° Fahrenheit.
- Package sample as appropriate for biologic material.

Required PBMC samples	Date of sample collection
Pretreatment (prior to phase "A")	
Steady state on treatment phase "A" (day 15-21, cycle#1)	
Steady state on treatment phase "B" (day 15-21, cycle#1)	

• Ship the sample and the information requested above on the same day it was obtained with Federal express overnight priority delivery to:

[name]
Pediatric Oncology Branch, NCI
[name]
[name],
Bethesda, MD 20892-1101

- Notify [name] prior to shipment of the sample ([contact], e-mail: [contact]).
- Do not ship samples for delivery on a weekend or Holiday.
- Samples must be received by [name] within 24 hours of obtaining the sample.

PROCESSING OF SAMPLES

- After arrival at the Pediatric Oncology Branch, NCI:
- Mononuclear cells will be separated using the ficoll technique.
- The number of mononuclear cells in the specimen will be determined.

• The samples will be processed for FPTase activity

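### The on-treatment FPTase blood sample has no set time relative to dose and no recorded draw time, which adds avoidable noise to the surrogate-marker objective

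*Combined protocol and SAP*

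**What the plan says.** Secondary objective 1.1.4 is to measure FPTase activity in tumor and PBMCs and "to assess the value of FPTase activity as a surrogate marker for the antiproliferative effect of R115777". Section 3.1.8 gives the schedule: "FPTase activity will be assessed in PBMCs pretreatment and once between days 15 and 21 of treatment (steady state) on cycle #1" of each phase. Section 3.4.7 repeats it: "PBMC should be collected pretreatment, and once between days 15 and 21 of treatment (steady state) on cycle #1 of each treatment phase". Appendix 7 and the Appendix 5 sample list use the same window. None of them gives a clock time or a time after dose.

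Appendix 5 specifies the tube label: "Label tube with: Patient initials, Patient ID number, date, treatment phase", followed by day of treatment. The sheet returned with the sample has one column to complete, "Date of sample collection".

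Four other parts of the plan bear on the point:

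- **Diary (Appendix 11A).** It has a field for the time of each morning and evening dose, a code for missed doses and a line for the reason. It goes to the Pediatric Oncology Branch, which also receives the blood samples.
- **Biopsy pairing (3.1.6, 3.1.8, 3.4.6, 3.4.7).** PBMCs are to be drawn together with any biopsy; 3.4.6 adds that this applies whenever possible.
- **Withheld drug (3.2, 3.3).** Patients with related grade 2 toxicity "should have R115777/placebo withheld until the toxicity resolves", and related grade 3 or 4 toxicity also leads to withholding. Drug stops one week before elective major surgery. Neither section mentions the FPTase sample.
- **Pharmacokinetics (1.2.7).** In adults: "The average accumulation ratio of R115777 was calculated at 1.1, and therefore minimal accumulation is expected on the q12 hr dosing regimen".

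**The concern.** Steady state means that the profile repeats from one interval to the next. It does not mean that the level is constant within an interval. A short half-life and minimal accumulation on 12-hourly dosing imply that most of each dose has gone before the next one, so the level at the draw depends on the hour of the draw.

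The schedule gives one on-treatment PBMC value per phase, and only one phase is on R115777. A patient therefore has at most one scheduled on-drug value, and timing error cannot be averaged out. If that error is material, a weak correlation between FPTase inhibition and tumor effect could not be told apart from a sampling artefact. Draw times that were never recorded cannot be recovered afterwards.

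**Working it through.** **Inputs, all from section 1.2.7 unless stated.** Dosing interval 12 h (3.1.3). Adult dominant half-life 2-3 h and accumulation ratio 1.1. Pediatric mean time to peak 2.7 h and mean terminal half-life 6.8 h. Pediatric AUC 4318 ± 1763 at 150 mg/m² and 13536 ± 7831 at 375 mg/m².

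**1. The plan's accumulation ratio.** R = 1/(1 − 2^(−12/t½)). A half-life of 2 h gives 1.02 and 3 h gives 1.07, which rounds to the stated 1.1. Solving R = 1.1 gives t½ = 12/log₂(11) = 3.47 h. I use 2.5, 3.5 and 6.8 h as the range.

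**2. Fall within one interval.** Pure decay from the 2.7 h peak to 12 h is 2^(9.3/t½): 13-fold at 2.5 h, 6.4-fold at 3.47 h and 2.6-fold at 6.8 h. A full steady-state one-compartment oral profile is gentler. With C(t) ∝ e^(−kt)/(1 − e^(−12k)) − e^(−ka·t)/(1 − e^(−12ka)), and ka set so that a single dose peaks at 2.7 h, the highest-to-lowest ratios are 6.4, 4.5 and 2.4.

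**3. Real between-patient spread.** CV = 1763/4318 = 41% and 7831/13536 = 58%. Log SD = √ln(1 + CV²) = 0.39 and 0.54.

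**4. Share of variance due to timing.** Draw times were taken as uniform over three windows, and the SD of log C(t) was computed on the full profile. Share = s²/(s² + b²), where s is the timing SD and b is the between-patient log SD of 0.39 or 0.54.

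| Draw window after dose | s at t½ 2.5 / 3.5 / 6.8 h | Share of variance | Factor on a correlation |
|---|---|---|---|
| Any hour, 0-12 h | 0.57 / 0.47 / 0.27 | 20-68% | 0.57-0.89 |
| Daytime, 1-9 h | 0.34 / 0.29 / 0.18 | 10-42% | 0.76-0.95 |
| Fixed, 2-6 h (illustrative) | 0.14 / 0.12 / 0.08 | 2-11% | 0.95-0.99 |

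The last column is √(b²/(s² + b²)).

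**5. On the inhibition scale.** Assume inhibition = C/(C + IC50), with 80% inhibition at the average concentration. Inhibition then runs over the interval from 52 to 87%, 59 to 87% or 70 to 85% for the three half-lives. The timing SD is 11, 8 or 5 percentage points, against 6-9 points from real exposure differences.

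**6. Withheld drug.** The fraction of the trough level left after a further 24 h is 2^(−24/t½): 0.1%, 0.9% and 9%. One week before elective surgery is 168/6.8 = 25 half-lives, so a specimen and paired PBMCs taken at such surgery are essentially drug-free.

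**The case against.** The strongest reply is that steps 4 and 5 are plasma pharmacokinetics standing in for enzyme data. The documents give no plasma-to-PBMC relation and no enzyme recovery rate. Their only inhibition figure, at least 80% at 300 mg q12h and above in adult leukemia (1.2.5), has no sampling time. Slow recovery would flatten the profile. Differences between patients in IC50 or enzyme level, and assay error, would all reduce timing's share. Blood is also shipped whole and separated on arrival, so the assay may not reflect the moment of the draw. Same-day dispatch by overnight courier makes daytime draws more likely than draws at any hour. All of this stands, and it limits the size that can be claimed.

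Four stronger readings are tempting, but the documents do not support them:

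- **A reader might infer that the plan permits sampling during a dose hold.** The wording places the sample on treatment at steady state, which implies that drug is being taken. What is missing is a rule for samples drawn when it is not.
- **A reader might infer that dose times are not recorded at all, so a held patient would be read as uninhibited.** The diary captures doses and missed doses. The missing items are the draw time and a link from sample to diary.
- **A reader might infer that PBMC and tumor values are misaligned.** The plan pairs the two draws, so they share their time since dose.
- **A reader might infer that timing swamps real differences.** On the inhibition scale the two are of similar size, and with daytime draws timing is the smaller part of the variance in every case computed.

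Section 5.4 specifies no FPTase analysis, so no pre-specified test is damaged. This bears on priority; it does not remove the gap.

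**Conclusion.** The point holds as a cheap improvement. The sample is fixed only to a seven-day window, and time since dose cannot be reconstructed from the records specified. Plasma concentration falls about 2.4- to 6.4-fold, or more, within an interval.

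If PBMC inhibition follows plasma level directly, timing accounts for about 10-42% of the variance in log concentration with daytime draws and 20-68% with any-hour draws. A correlation with tumor effect would then be multiplied by roughly 0.76-0.95 or 0.57-0.89. These ranges rest on half-lives of 2.5-6.8 h, the AUC spreads in 1.2.7, uniform draw times and the direct-effect assumption. They show what is possible; they do not measure what will happen. Since enzyme recovery is unknown, recording the times is also what would let the trial check whether timing matters.

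Only secondary objective 1.1.4 is affected. Placebo-phase samples and the primary time-to-progression analysis are not.

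**What to change.** - **Appendix 5:** add draw time and date/time of last dose to the tube label and the collection sheet.
- **Sections 3.1.8 and 3.4.7:** set one dose-relative sampling window within days 15-21. Trough or a fixed post-dose window would both serve; the 2-6 h case above is only an illustration. Keep the PBMC draw paired with the biopsy.
- **Samples drawn off drug:** identify them from the diary, flag them, and leave them out of the on-treatment inhibition analysis. Moving the draw to the next cycle is less attractive, because it could follow a dose reduction under 3.3 and separate the sample from its biopsy.
- **On-drug samples outside the window:** keep them, with time since dose as a covariate or in a sensitivity analysis. Discarding them would cost data in a trial sized at 60 patients.

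The cost is two form fields and some scheduling of one visit per phase. No dosing or hold rule changes.

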3.1.9 Nerve Growth Factor (NGF)

A blood sample will be collected pretreatment, and then prior to cycles 4, 7, 10, and then after every six cycles on treatment phase ("A" and "B"). NGF levels will be correlated with the development of clinical neurotoxicity (Appendix 6).

3.1.10 Monitoring Toxicity

The hematologic and non-hematologic toxicities of R115777 will be monitored and recorded throughout treatment with R115777 or placebo. (Appendix 1 and Sections 3.4 and 3.7). The Cancer Therapy Evaluation Program Common Toxicity Criteria (CTC) Version 2.0 will be used for toxicity assessment. A copy of the CTC version 2.0 can be downloaded from the CTEP home page at http://ctep.cancer.gov (Section 5.3).

3.2 Drug Administration

R115777 or placebo in 50 mg tablets will be manufactured by Janssen Pharmaceuticals and supplied by CTEP, NCI under IND #58359. Tablets will be administered orally immediately after a meal every 12 hours for 21 days followed by a 7 day rest period (28 day cycles). The dose of R115777or placebo will be 200 mg/m² every 12 hours, and is based on the maximum tolerated dose on the intermittent dosing schedule from the pediatric phase I trial. See Section 2.2.1 for calculation of BSA. Each patient's dose will be rounded to the nearest 50 mg according to the following dosing table:

BSA (m²)	R115777 / Placebo	R115777 / Placebo
	(mg po q12h)	(# of 50 mg tablets po q12h)
0.00 - 0.37	50	1
0.38 - 0.62	100	2
0.63 - 0.87	150	3
0.88 - 1.12	200	4
1.13 - 1.37	250	5
1.38 +	300	6

Tablets may be crushed for easier consumption in young children.

R115777/placebo should be re-taken if vomiting occurs within 30 minutes of taking the dose.

Patients who have to undergo an elective major surgical procedure (not to include the biopsy of discrete neurofibromas requested on this protocol) should stop taking study drug one week before the surgery, and are allowed to resume study drug 2 weeks after surgery, provided they have recovered from the procedure.

3.3 MODIFICATIONS FOR TOXICITY

Patients who experience **grade 2 toxicity** (CTC v. 2) related to R115777 or placebo should have R115777/placebo withheld until the toxicity resolves (grade \leq 1) and then restarted at the same dose level. If the grade 2 toxicity recurs, the R115777/placebo dose should be withheld again until the toxicity resolves (grade \leq 1) and then reduced by 50 mg per dose. For patients with a BSA \leq 0.37 the dose will be reduced to 50 mg once daily. If the grade 2 toxicity recurs the patient should be taken off protocol. If a grade 2 toxicity persists for >10 days off therapy, the patient should be discussed with the PI.

Patients who experience **grade 3 or 4 toxicity** related to R115777 or placebo should have their dose withheld. If the toxicity returns to grade ≤ 1 within 10 days, patients may resume R115777/placebo at a dose reduced by 50 mg per dose. For patients with a BSA ≤ 0.37 the dose will be reduced to 50 mg once daily. If the toxicity persists at grade ≥ 2 for >10 days without administration of R115777/placebo or the grade 3 or 4 toxicity recurs at the lower dose level, the patient should be removed from the study (see Section 3.6.2).

If the toxicity warrants, the physician can determine whether the patient is receiving R115777 or placebo (unblind the study) by calling [name] [contact] or [name] [contact]. These physicians can also be reached through [contact] or the NIH page operator [contact] (see section 8.2.5). Pediatric Oncology Branch staff will require the protocol number (i.e., 'T99-0090'), the patient's ID number (e.g., '00-C0222-01'), the phase (i.e., 'A' or 'B'), and the patient's

initials (first three letters of last name, eg., 'ABC') to unblind the patient. The unblinded patient must be removed from the study.

3.4 ON STUDY EVALUATION (SEE APPENDIX 7)

- 3.4.1 HISTORY & PHYSICAL EXAMINATION: Every 2 weeks during the first 3 cycles on each treatment phase ("A", "B"). Physical exam should include assessment of performance status (documentation if changed from baseline), measurement of visible or palpable neurofibroma, height, weight and body surface area prior to every treatment cycle. A complete neurologic examination should be performed and focus on signs of sensory peripheral neuropathy. After cycle 3 perform prior to each cycle. History and physical examination will be documented in case report forms as outlined Section 5.1.1.
- 3.4.2 Photography: When possible, plexiform neurofibromas that are visible on the body surface should be photographed prior to treatment cycle 1, 4, 7, 10, and then after every 6 cycles on each treatment phase ("A", "B"). A size marker should be taped to the skin in the field of view when appropriate, and the plexiform neurofibroma will be photographed so that it fills the frame. Frontal and side images will be taken, as appropriate. Copies of photographs identified by the patient ID number, date, treatment phase ("A" or "B"), and treatment cycle should be sent to:

[name], R.N.
Pediatric Oncology Branch, NCI
[name]
[name]
Bethesda, MD 20892-1928

3.4.3 LABORATORY ASSESSMENT (see Appendix 7). Laboratory studies will be documented in case report forms as outlined Section 5.1.1.

Hematology: During the first 3 cycles of treatment on each treatment phase ("A", "B"), obtain complete blood count, differential and platelet count every other week (more frequent monitoring may be performed if the ANC <1,000/mm³ or platelet count <50,000/mm³). During subsequent cycles complete blood count, differential, and platelet count will be obtained prior to each cycle. PT, PTT and fibrinogen will be obtained prior to each treatment phase.

Chemistries: During the first 3 cycles of treatment on each treatment phase ("A", "B"), obtain electrolytes, creatinine, calcium, magnesium, phosphorus, SGPT, and bilirubin every other week. During subsequent cycles these tests should be performed prior to each treatment cycle.

Urinalysis: Prior to treatment cycle 1, 4, 7, 10, and then q 6 cycles on each treatment phase ("A", "B").

3.4.4 RADIOGRAPHIC EVALUATION: Evaluate the index lesions by MRI prior to cycle 1 on treatment phase "A", and prior to cycle 4, 7, 10, and then after every 6 cycles on each treatment phase ("A", "B"). The protocol outlined in Appendix 1 will be used each

time MRI examinations are performed to assess progression or response to R115777 or placebo. In patients with clinical suspicion of disease progression MRI analysis should be performed earlier using the protocol outlined in Appendix 1. At the time of disease progression on treatment phase "A", if possible, a MRI scan of all known measurable plexiform neurofibromas in addition to the index lesions should be performed, in order to have a new baseline prior to treatment phase "B" (Appendix 1).

- 3.4.5 OPHTHALMOLOGIC EVALUATION: Prior to or within the first three days of starting treatment phase "A", and prior to or within the first 3 weeks of starting treatment phase "B". Exam should include visual fields if the patient is able to cooperate with the exam and examination of the lens for opacifications.
- 3.4.6 TISSUE PROCUREMENT: In patients with easily accessible discrete neurofibromas or superficial plexiform neurofibromas, who consent to the procedure, biopsies will be performed prior to the first dose of treatment on phase "A", and if feasible at one steady state time point on each treatment phase ("A", "B") (between day 15-21 on cycle #1) of treatment. In addition, attempts will be made to obtain tumor specimens from any patients requiring surgery for complications of their tumors or for unrelated medical problems. Peripheral blood mononuclear cells for FPTase assay (Section 3.4.7, appendix 5) should be obtained at the same time as biopsy whenever possible. As this is an invasive procedure, patients may refuse biopsy and still be eligible for the study.

Two kits will be supplied for handling and shipping of tumor specimens. To obtain the kits, please call [name] [contact]. Kits will be sent by FedEx to arrive several days prior to the surgical procedure. Included in the kits will be all media and tubes needed for shipment. Procedures for tissue handling and shipment are provided in Appendices 3 and 4, respectively.

- 3.4.7 FPTase ACTIVITY IN PBMC: PBMC should be collected pretreatment, and once between days 15 and 21 of treatment (steady state) on cycle #1 of each treatment phase ("A" and "B"). If the patient has consented to a tumor biopsy, PBMCs should be obtained at the same time as the biopsy (Section 3.4.6). PBMC should be separated from 20 ml of blood (10 ml in children \leq 10 kg) as described in Appendix 5.
- 3.4.8 Nerve Growth Factor: A blood sample will be collected pretreatment, and prior to cycles 4, 7, 10, and then after every six cycles on each treatment phase ("A", "B"). Nerve growth factor levels will be correlated with the development of clinical neurotoxicity (Appendix 6).
- 3.4.9 QUALITY OF LIFE (QOL) ASSESSMENT: The National Institutes of Health (NIH) Impact of Pediatric Illness (IPI) Scale, which assesses the impact of disease and treatment on children's behavior, should be administered to all patients ≥6 years to 18 years of age and their primary caregiver prior to the start of therapy, and then prior to cycles 4, 7, 10, and then after every 6 cycles on each treatment phase. This questionnaire has not been completely validated, and means and standard deviations for different subgroups of patients on the scale and subscales are not available yet. This assessment

consists of an age-appropriate questionnaire and generally takes less than 30 minutes to complete. Patients between the ages of 6 and 10 years of age should be administered the IPI-Young Child form; patients between 11 and 18 years of age should be administered the IPI-Older Child/Adolescent form; the patient's primary caregiver should receive the IPI-Parent Form. This questionnaire will not be administered to patients > 18 years. Patient and parent response forms should be photocopied after completion and copies sent to [name], Pediatric Oncology Branch, NCI, [contact], [name], Bethesda, MD 20892-1928 within 2 weeks of completion of the cycle of therapy. Any questions regarding the administration of the IPI Scale should be addressed to [name]. at [contact], e-mail: [contact].

